4.1. Study Procedure

Trial clinicians will contact all participants referred to the trial to schedule an initial face-to-face screening interview. During the initial interview, the trial clinicians establish written consent, that inclusion criteria are satisfied, and confirm the diagnosis using the (SCID-5-RV). All randomised participants will receive two 500mg mangosteen pericarp capsules once a day to a total dose of 1000mg daily (or placebo) with food, in addition to treatment as usual. The mangosteen pericarp and placebo will be encapsulated and matched in appearance. Dose changes to existing medications (either increases or decreases in dose) or switch in medication will be accepted, documented and participants will be allowed to continue on the trial.

4.2. Exposure measures - Garcinia mangostana Linn & Placebo

From visit one, participants will be instructed to return unused medication. The amount of medication dispensed and returned will be calculated and documented. This data will be used to calculate compliance with medication for analysis purposes.

4.3. Enrolment Demographic Variables

The following variables will be assessed for enrolment in the study and for demographic purposes:

- Demographics (age, gender, marital status, educational attainment)
- Onset of prodromal symptoms

- Duration of current episode and illness
- Age at first episode and number of previous episodes
- Frequency of hospital admissions and any precipitating factors
- Presence of comorbid disorders and other axis I and II disorders (DSM-5)
- Medical history
- Current and previous medication
- Family psychiatric history
- Smoking, alcohol and illicit substance behaviours
- Use of dietary supplements

4.4. Efficacy Variables

The primary outcome variable will be the MADRS total score at the end of the 24-week treatment phase.

Secondary outcomes include the Bipolar Depression Rating Scale (BDRS), Young Mania Rating Scale (YMRS) and Hamilton Anxiety Rating Scale (HAM-A) scores. Participant life satisfaction will be rated on the self-reporting scale (Q-LES-Q). Functioning measures will include the Social and Occupational Functioning Assessment Scale (SOFAS), and Longitudinal Interval Follow-Up Evaluation-Range of Impaired Functioning Tool (LIFE-RIFT). The Clinical Global Impressions Bipolar Version (CGI-BP) will be used to rate clinician judgement for improvement and severity of illness. The Patient Global Impression Scale (PGI) will be used to rate participant perception. We will ask participants to complete a number of pen and paper based cognitive tasks; digit span forwards and backwards, trail making and the Symbol Digit task.

In order to undertake a cost-utility analysis (CUA), gains in utility for the participants will be measured in the study. The most common metric developed to measure utility gains from health interventions is the QALY. A QALY is simply calculated by multiplying the period of time spent in a particular health state by the "utility" or preference value assigned to that health state measured on a scale from 0 (denoting death) to 1 (denoting full health). There are different techniques of deriving utility however the simplest is via the use of a multi-attribute utility instrument which is basically a health related quality of life measure (HRQoL) which has pre-determined "weights" assigned to the health states included within the measure – this is called indirect elicitation of utility. We propose to use the AQol4D to assess any utility based HRQoL gains. It comprises four separately scored dimensions, consisting of independent living, relationships, mental health, and senses. It consists of 12 items and takes 2 minutes to complete. The main utility algorithm of the AQoL has been scored using the time trade off method and the questionnaire has sound psychometric properties. The AQoL4D will be administered to study participants at baseline, 12 and 24 weeks. Scoring will be completed with the algorithm provided by the developers of the instrument obtained from: http://www.aqol.com.au/scoring-algorithms.html .

To measure the healthcare services used by participants during the course of the trial, but outside of the study assessments, a resource use questionnaire (RUQ) will be employed. The RUQ will ask participants to provide information on hospitalisations, consultations with health care providers, and other related health

services utilised. The RUQ also asks questions regarding lost paid and upaid productivity. The data collected will combined with other data derived from the trial (i.e. medications utilised) and then valued using standard Australian unit costs from the Medicare and Pharmaceutical Benefits Schedules, the Independent Hospital Pricing Authority, and wage rates from The Australian Bureau of Statistics.

4.5. Assessment of inclusion and exclusion criteria

4.5.1. Inclusion Criteria

- Aged 18 years or older,
- Have a DSM-V diagnosis of bipolar disorder I or II, or bipolar disorder not elsewhere classified (NEC),
- Currently be in a major depressive episode on SCID-5-RV
- Score at ≥ 20 on the MADRS
- Participants currently under therapy for bipolar disorder will need to have been on that primary therapy for at least four weeks prior to randomization,
- Have the capacity to consent to the study and comply with study procedures,
- Be using effective contraception if female, sexually active and of childbearing age,
- Be able to speak, read, write and understand the English language,
- Participants will be required to nominate a current treating physician and will not be eligible to enter the study until one is identified.
- If a researcher is in doubt at any time about an inclusion criterion point please consult an investigator.
- If the is a delay of >7 days between screening and baseline assessments, or baseline assessment and medication commencement, the inclusion scale (MADRS) should be administered again to ensure the participant still meets eligibility criteria.

4.5.2. Exclusion Criteria

- Participants with a known or suspected active systemic medical disorder,
- Individuals who are pregnant or lactating (participants will be requested to conduct a urine pregnancy test if sexually active and of child-bearing age),
- Participants currently enrolled in any other intervention study will be excluded,
- Individuals who are intolerant, allergic to or have had an anaphylactic reaction to any components of the preparation,
- Inability to comply with either the requirements of informed consent or the treatment protocol.

4.6. Withdrawal Criteria

Withdrawal from the trial will occur if the participants cease taking their trial medication for seven consecutive days or if the participants cease effective contraception or becomes pregnant or if the participant commences new Electroconvulsive Therapy (ECT) treatment. Dose changes to existing medications (either increases or decreases in dose), or addition or removal of an agent will be accepted and participants will be allowed to continue with the trial. Participants will be withdrawn from the study if they withdraw consent or at the discretion of the researcher given adverse events or loss to follow-up. Serious adverse events will not require automatic withdrawal from the study.

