6.8. Withdrawal of participants from treatment or assessment

Participants will be withdrawn from the trial if they; discontinue the trial medication for >7 days; cease effective contraception, become pregnant or withdraw consent.

Discontinuation due to adverse events (both serious and non-serious) may be a criterion for withdrawal, but is not mandatory, and could be either at the request of the participant or the discretion of the investigator. Withdrawal of consent will not require any data to be destroyed. This instead is termed 'revocation of consent' and has an associated form to be completed.

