9.1. Description of analysis sample

The sample to be included in the analyses will be all the participants who give consent to participate in the study who meet all inclusion criteria and no exclusion criteria, and who have taken at least one dose of trial medication and completed at least one post-baseline assessment.

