9.2. Method of statistical analysis

All analyses will be conducted in accordance with the International Conference on Harmonization E9 statistical principles, and are based on all randomised participants with at least one post-baseline observation (intention to treat population). Reporting of research findings will be done in accordance to CONSORT guidelines. The statistician responsible for the analysis of outcome data will be blind to group allocation. The primary efficacy analysis will assess average treatment group differences for the primary outcome measure MADRS total score over the entire study period and will use a likelihood based mixed-effects model, repeated measures approach (MMRM). The MMRM model includes the fixed, categorical effects of treatment, investigator, visit, and treatment-by-visit interaction, as well as the continuous, fixed covariates of baseline score and baseline score-by-visit interaction. The MMRM includes all available data at each time point and is the preferred method of analyzing clinical trial data in psychiatry as compared to more traditional repeated measures analysis of variance (ANOVA) and analysis of covariance models (ANCOVA). Planned comparisons will be done with the MMRM models to determine between group differences in change of symptoms measures from baseline to week 24. Results from the analysis of dichotomous data will be presented as proportions, with 95% confidence interval, and Fisher's exact p-value where appropriate. Non-parametric statistics will be used when assumptions for parametric methods are violated. Effect sizes will be calculated using Cohen's guidelines. All tests of treatment effects will be conducted using a two-sided alpha level of 0.05 and 95% confidence intervals. Change scores in symptoms and in biological markers will be derived. Pearson Product Moment Correlations will be used to examine the relationships between the change scores for symptoms and the change scores for biological markers in the two groups. Using Fisher's z transformation, we will test whether the correlations obtained for each group are statistically different in terms of strength.

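### Sections 4.6 and 6.8 take participants out of the trial, not only off treatment, after about seven days without capsules, and nothing provides for later MADRS ratings

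*Protocol*

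**What the plan says.** Section 4.6 (Withdrawal Criteria): "Withdrawal from the trial will occur if the participants cease taking their trial medication for seven consecutive days". It also lists stopping contraception, pregnancy and new ECT. By contrast, people whose background medication changes may carry on in the trial, and a serious adverse event does not force withdrawal.

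Section 6.8: "Participants will be withdrawn from the trial if they; discontinue the trial medication for >7 days". It also lists contraception, pregnancy and withdrawal of consent, but not ECT. Its heading is "Withdrawal of participants from treatment or assessment", yet the text beneath gives no route for leaving treatment while staying in assessment.

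Section 4.4 sets the endpoint: "The primary outcome variable will be the MADRS total score at the end of the 24-week treatment phase". Section 9.1 limits the analysis sample to eligible, consenting participants "who have taken at least one dose of trial medication and completed at least one post-baseline assessment". Section 9.2 applies the intention-to-treat label to randomised participants with at least one post-baseline observation. It directs the primary analysis at "average treatment group differences for the primary outcome measure MADRS total score over the entire study period", with a planned week-24 comparison, and adds: "The MMRM includes all available data at each time point".

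**The concern.** Stopping capsules and starting ECT both happen after randomisation, and both are plausibly related to how the participant is doing. If ratings end there, week-24 MADRS is missing for these people because the protocol does not ask for it, not because they refused it. The mixed model fills the gap by assuming that, given their earlier scores, they would have gone on like similar participants who stayed. If benefit fades once capsules are stopped, that assumption gives a different answer from the effect in everyone randomised.

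Someone actually withdrawn before the week-4 assessment has no post-baseline score and so leaves the analysis set of 9.1 and 9.2.

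This cannot be left to the statistical analysis plan. A plan can add sensitivity analyses, but what is collected is fixed by the protocol.

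**Working it through.** **1. Are MADRS ratings provided for after withdrawal?** The places where such a provision could stand:

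| Place | What it provides after withdrawal |
|---|---|
| 4.6, 6.8 | Withdrawal from the trial; no separate off-treatment follow-up |
| 6.3, 6.8 | Data already collected are kept when consent is withdrawn; no new ratings |
| 6.7 | Skipped-visit rule for late attendance; nothing for withdrawn participants |
| 6.13.2.2 | Adverse events only, for at most 7 days unless the physician or investigator extends it |
| 7.2 | Pregnancy outcome only, to week 28 |
| Table 1 | No column for withdrawn participants |

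None provides for MADRS. The protocol does not say outright that ratings stop, but this is the natural reading, because 4.6 sets withdrawal against being allowed to continue.

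**2. The plan's own figure.** Section 9.3 needs 120 participants and allows for 20% attrition: 120 / (1 - 0.20) = 150, as stated. This reproduces the target but does not test the concern. The 20% is typical attrition in earlier trials; it is neither a rate for this rule nor a bound on it.

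**3. Size at week 24.** Inputs: d = 0.362 (9.3), used only as a scale; s = share of the active arm that stops, *assumed* 5-20%; k = share of the benefit kept after stopping, *assumed* 0-100%. The gap is the missing-at-random estimate minus the effect in all randomised:

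gap = s × (1 - k) × 0.362

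| s | k = 0 | k = 0.5 | k = 1 |
|---|---|---|---|
| 5% | 0.018 | 0.009 | 0 |
| 10% | 0.036 | 0.018 | 0 |
| 20% | 0.072 | 0.036 | 0 |

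**4. Size for the study-period average.** With a constant effect and m of the six post-baseline visits missed, the average gap is the week-24 gap × m/6. In the worst case (s = 20%, k = 0):

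- m = 1: 0.072 × 1/6 = 0.012
- m = 3: 0.072 × 3/6 = 0.036
- m = 5: 0.072 × 5/6 = 0.060

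A simulation of this worst case (200,000 per arm, six visits, correlation 0.5) agreed: about 0.072-0.073 at week 24, and about 0.012, 0.036 and 0.060 for the average.

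**5. Against the standard error.** 120 participants at 1:1 give 60 per arm.

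- Week 24: SE = sqrt(2/60 + 0.362²/(4 × 60)) = 0.184, and 0.072 / 0.184 = 0.39.
- Average of six visits at an *assumed* within-person correlation of 0.5: SE = 0.184 × sqrt((1 + 5 × 0.5)/6) = 0.184 × sqrt(3.5/6) = 0.14, before baseline adjustment and missing data. Then 0.036 / 0.14 = about 0.26.

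**6. What the figures leave out.** They model only lost benefit among active-arm stoppers. The sign can reverse if placebo stoppers fare worse than the model predicts. People withdrawn before week 4 are not quantified.

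**The case against.** The strongest reply is that the text is ambiguous rather than wrong. The heading of 6.8 offers treatment and assessment as alternatives, and 7.2 ends study drug in pregnancy while still following the outcome, so one trigger does not end all contact. This stands in part: the protocol never forbids later ratings. But a site following 4.6 and 6.8 would stop rating, and the same amendment is needed on either reading.

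A reader might infer that everyone who stops capsules before week 4 is excluded from the analysis. The documents do not support that. Adherence is judged from returned capsules and contact is described at 4-weekly visits, so a person who stops early but attends week 4 would ordinarily be identified there, where MADRS is due. Exclusion needs an earlier withdrawal, and a person who simply does not attend loses the score under any rule.

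A reader might also infer that the rule contradicts the intention-to-treat label. It does not. Section 9.2 defines its own set, participants with a post-baseline score stay in it, and available data means data that exist. Whether off-capsule scores belong in the primary model is partly an estimand choice.

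Finally, the rule is narrow. Medication changes, serious adverse events and skipped visits do not trigger it, and stopping that depends only on observed MADRS is compatible with the model. These points limit the size of the problem; they do not supply the missing scores.

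**Conclusion.** The point holds as an avoidable loss of outcome data. It is worth correcting but is not a fatal flaw. It rests on the natural reading of 4.6 and 6.8 and on the absence of any provision for MADRS afterwards.

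The effect is modest. Under the assumed 5-20% stopping and 0-100% retained benefit, the week-24 gap is 0 to 0.072 SD, at worst about 0.4 standard errors. For the study-period average with three visits missed, the worst case is 0.036 SD, about 0.26 standard errors at the assumed correlation. A middle case (10% stop, half the benefit kept) gives 0.018 SD at week 24. The direction is not fixed. This is a matter of validity, not of power. Confidence is medium, because the stopping rate is unknown and the protocol does not state in terms that ratings end.

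**What to change.** In 4.6 and 6.8, separate stopping trial medication from leaving the study. Participants who stop capsules, cease contraception, become pregnant or start ECT come off capsules where required but continue the scheduled MADRS visits to week 24, by the remote route in 6.7 if needed, unless they withdraw consent to follow-up. Use one identical trigger list in both sections; at present they differ on seven days versus more than seven, and only 4.6 names ECT.

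The statistical analysis plan should state how scores after stopping capsules and after ECT enter the primary analysis. Including off-capsule scores is the natural choice given the intention-to-treat label.

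Cost: a short amendment to two sections. If 5-20% of 150 stop (7.5 to 30 people) and each keeps one to six visits, that is 7.5 × 1 = about 8 to 30 × 6 = 180 visits, or 0.6-15% of the 150 × 8 = 1,200 already scheduled. At up to $20 each, reimbursement is about $150 to $3,600. At 40-60 minutes each, interview time is about 5 to 180 hours. The downside is visit burden for people no longer taking capsules, and some will decline.

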5.3. Study Design

This is a 24-week, double blind, randomised, placebo-controlled trial of adjunctive *Garcinia mangostana* Linn in the treatment of bipolar depression (n=150). The duration of the current trial will be 24 weeks concordant with our pilot data. A follow-up interview will be scheduled 4 weeks after completion of the study. The trial will be conducted following approval from the relevant ethics committees, and conducted in accordance with the Good Clinical Practice guidelines. The trial will be conducted according to Australian Clinical Trial guidelines and the National Ethical guidelines for Human Research. This protocol was developed in accordance with Standard Protocol Items Recommendations for Intervention Trials (SPIRIT) 2013 guidelines, and findings will be reported using CONSORT guidelines. All participants will give informed consent prior to enrolment. Participants will be withdrawn from the study if they withdraw consent or at the discretion of the investigators.

6. Procedure

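### The contraception withdrawal rule acts on stopping contraception, not on being sexually active without it, and no check is scheduled after baseline (minor participant-safety gap)

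*Protocol*

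**What the plan says.** **Entry.** Protocol 4.5.1 lists among the inclusion criteria: "Be using effective contraception if female, sexually active and of childbearing age". Under 4.5.2, "participants will be requested to conduct a urine pregnancy test if sexually active and of child-bearing age". Table 1 shows the pregnancy test for females at visit 1 only. Its footnote makes the test non-compulsory for a participant who is not sexually active, or where the treating clinician sees no need. Section 6.14 also places the urine test at baseline.

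**After entry.** Section 4.6 requires withdrawal "if the participants cease effective contraception or becomes pregnant". Section 6.8 lists the same events: "cease effective contraception, become pregnant or withdraw consent". Section 7.2 stops study drug at once when pregnancy occurs.

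**Related provisions.** Section 4.5.1 adds: "If a researcher is in doubt at any time about an inclusion criterion point please consult an investigator". Section 5.3 states: "Participants will be withdrawn from the study if they withdraw consent or at the discretion of the investigators". Sections 4.7 and 6.13.2.1 provide for open questions about general health and health problems, and Table 1 has concomitant medication reviewed at every visit. Medication is dispensed six times (6.10), at weeks 0, 4, 8, 12, 16 and 20 (Table 1).

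**The concern.** The entry rule depends on a status: sexually active, of childbearing age, using contraception. The withdrawal rule depends on an event, stopping contraception. The two agree only for women who were already using contraception at entry. For others the withdrawal rule errs in two directions:

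- It misses a woman who used no contraception at entry because she was not sexually active, and who later becomes sexually active without it. She cannot stop what she never started.
- It catches a woman who stops contraception because she is no longer sexually active and is not at risk.

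No item in the visit schedule is designed to detect either change. The protocol excludes pregnant women, requires contraception and stops drug on pregnancy, so it plainly means to avoid exposure in pregnancy. Followed as written, it can leave a woman at risk of pregnancy on the agent until she mentions the change, an investigator uses discretion, or a pregnancy becomes known.

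**Working it through.** The plan gives no figure on this point. The check sets the rules side by side and then counts visits.

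**Step 1: which mandatory contraception rule applies to whom**

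| Participant of childbearing age | Entry rule (4.5.1) | Mandatory contraception trigger (4.6, 6.8) |
|---|---|---|
| Sexually active, using contraception, then stops while still active | Met | Applies, as intended |
| Using contraception, then stops because no longer sexually active | Met | Applies, though she is not at risk |
| Not sexually active, no contraception, stays so | Not required | None, and none needed |
| Not sexually active, no contraception, then active without it | Not required | None until pregnancy |

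Nothing in 4.5.1 says that the criterion is reapplied after randomisation, and Table 1 shows the inclusion and exclusion check at visit 1 only.

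**Step 2: scheduled checks**

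- Dispensations at weeks 0, 4, 8, 12, 16 and 20: 6 in all, so 6 − 1 = 5 after baseline.
- Contraception or pregnancy checks scheduled after week 0 in Table 1 and 6.14: 0.
- The existing trigger therefore has no item of its own to detect it. The concomitant-medication review might show that a drug method was stopped. It would not show that a non-drug method was stopped, or that no method was ever used.

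**Step 3: longest undetected interval as planned**

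For a change just after week w, the treatment time left is 24 − w.

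- w = 0, 4, 8, 12, 16, 20 gives 24, 20, 16, 12, 8, 4 weeks.

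The ceiling is 24 weeks.

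**Step 4: the same interval with one question before each later dispensation**

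Section 6.7 allows visits within 1 week of the due date. A visit later than that is a deviation but can still take place. It is skipped only if it cannot happen before 2 weeks from the due date. Lateness can therefore approach 2 weeks.

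- Nominal: 4 weeks.
- From baseline, next visit up to 2 weeks late: 4 + 2 = 6 weeks.
- Between later visits, one a week early and the next up to 2 weeks late: 4 + 1 + 2 = 7 weeks.
- One visit skipped: 8 + 2 = 10 weeks from baseline, or 8 + 1 + 2 = 11 weeks between later visits.

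These are calendar intervals between checks. They equal time on drug only if supply continues. Because medication is dispensed monthly, a skipped visit may leave a participant without capsules. For a change after week 20 the added question brings no gain.

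**The case against.** Several provisions soften the gap. Pregnancy is itself a mandatory trigger and stops drug at once. Investigators may withdraw a participant at their discretion. A researcher in doubt about an inclusion criterion is told to consult an investigator. Health and concomitant medication are reviewed at each visit. These leave a smaller residual risk but do not close the gap. Discretion and consultation work only once someone knows, a new sexual relationship is not a health problem that an open question would draw out, and the pregnancy trigger acts after the event the contraception rule is meant to prevent.

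It can also be said that a scheduled question, or a duty to report a change, might sit in the consent pages or the case report form. Neither is shown, so the point is confined to the wording of 4.6 and 6.8 and the schedule in Table 1 and 6.14. Withdrawal rules and visit schedules are protocol content and are not matters left to a SAP.

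Stronger readings are tempting and are not supported:

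- A reader might infer that participants face a known reproductive hazard. The protocol gives no reproductive data on the agent. Section 2.5 reports no difference in adverse events in the pilot trial.
- A reader might infer that a woman who is not sexually active is barred from a baseline pregnancy test. Table 1 lists the test for females, and the footnote only makes it non-compulsory.
- A reader might take 24 weeks as the expected exposure. It is a ceiling, reached only if her status changes just after baseline.
- Section 4.6 sets the discontinuation limit at "cease taking their trial medication for seven consecutive days" and section 6.8 at "discontinue the trial medication for >7 days". This is a separate inconsistency and adds no weight here.

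**Conclusion.** The point holds as a minor participant-safety gap. The mandatory contraception trigger is keyed to the wrong event: it misses a woman who becomes sexually active without contraception and, read literally, withdraws one who no longer needs it. No contraception or pregnancy check is scheduled across the five dispensations after baseline.

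The size can be given only in time. The undetected interval is up to 24 weeks as planned. With the added question it is about 4 weeks nominally, about 6 to 7 if visits run up to 2 weeks late, and about 10 to 11 if one visit is also skipped and supply continues. How many women this affects cannot be estimated, because the protocol gives no sex or age mix. A reader might infer harm to the trial's result, but the documents do not support that: the sample size does not depend on this rule, and at most an occasional extra withdrawal would follow from correcting it.

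**What to change.** 1. In 4.6 and 6.8, replace the trigger on ceasing contraception with a current-status rule: *A female participant of childbearing age who is sexually active and not using effective contraception has trial medication withheld until effective contraception is in place and a urine pregnancy test is negative. She is withdrawn if this is not achieved within the 7-day discontinuation limit.*
2. Keep pregnancy as a separate trigger with immediate stop of drug.
3. Add one line to Table 1: contraception status in females of childbearing age, asked before dispensing at weeks 4, 8, 12, 16 and 20.
4. When the text is amended, state the 7-day limit in the same words in both sections, so that the hold has one end point.

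**Cost**

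- *Questions:* at most five per woman at existing visits. If 20% to 50% of the 150 participants are women of childbearing age (an assumption), that is 30 to 75 women, or 5 × 30 = 150 to 5 × 75 = 375 short questions in the whole trial.
- *Tests:* an occasional urine pregnancy test, needed so that drug is not restarted after unprotected exposure without one.
- *Treatment time:* a hold of up to 7 of 24 × 7 = 168 days, or 7/168 = 4.2%, for each hold.
- *Withdrawals:* a rare extra one. Each uses 1 of the 150 − 120 = 30 places allowed for attrition in 9.3, or 3.3%. The visits she has completed stay in the mixed model of 9.2.
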